Title: Transcranial Infrared Laser Stimulation (TILS) of Prefrontal Cognition in Post-traumatic Stress Disorder (PTSD)

NCT number: NCT03209882

Date: 05/15/2021

Study Protocol

Veterans with PTSD are recruited from local community. Potentially qualified veterans will first undergo a diagnostic clinical interview (visit 1). The PTSD symptom scores and other medical information collected in this visit will be reviewed immediately to determine whether eligibility criteria are met. Eligible individuals will be guided to go through an IRB-approved informed consent form that describes the study and the terms of potential participation in the study. If a person chooses to participate, s/he will be scheduled for an fNIRS screening (visit 2). This screening will confirm whether the veteran shows hypoactivations in the prefrontal cortex in the memory retrieval phase – a precondition for study inclusion.

Table 1. Experimental protocol

Aim	Visit	Task
Evaluations & screening	1	Clinical evaluation and consenting
	2	fNIRS scan
Aim 1	3–4	Pre-treatment fNIRS scan Sham or TILS; bbNIRS measurement Post-treatment fNIRS scan
Aim 2	5–9	Pre-treatment fNIRS scan TILS; bbNIRS measurement Post-treatment fNIRS scan

Veterans who pass the initial evaluations and screening will be instructed to receive once weekly TILS treatment at the same light power for seven weeks (visits 3 – 9). In fact, we will administer a sham treatment and a TILS treatment in a randomized sequence during the first two weeks (visits 3 and 4) to determine any acute neurophysiological effects of TILS compared with those induced by sham. Specifically, these effects include: 1) the prefrontal metabolic/CCO changes measured by bbNIRS during the treatment; and 2) the incremental changes of prefrontal activations and scores from three neutral memory tasks, which will be measured by fNIRS before and after the treatment (i.e., post-treatment measures minus pre-treatment measures). Then, statistical analyses will be conducted to determine the acute neurophysiological effects of TILS compared with sham.

After the first two sessions, we will administer another five TILS treatments to the veterans (visits 5 – 9) with fNIRS and bbNIRS measurements taken in each visit. Thus, each veteran will receive a total of six TILS treatments. An iterative statistical analysis procedure will be implemented to determine the least number of TILS sessions that can stably up-regulate prefrontal activity, which will be considered as an optimal TILS dosage.

### Statistical Analysis Plan

TILS/sham-induced changes in HbO2, Hb and CCO concentrations from the initial baseline will be calculated using the UCLn algorithm. We will focus on oxidized CCO concentration because it is directly related to the oxygen metabolism at the cellular level. The mean CCO changes during the treatment period will be analyzed with repeated measures ANOVA (analysis of variance), by using treatment type (TILS, sham) as a within-subject variable and sex (male, female) as an independent variable.

An iterative statistical analysis will be implemented to determine whether the  $i$ th TILS treatment ( $i \leq 6$ ) is sufficient to stably up-regulate the veteran's prefrontal activations and functioning, by interrogating the veterans' incremental changes (post-treatment minus pre-treatment) in the prefrontal activations and behavioral scores in the three memory tasks. Specifically, at the  $i$ th iteration, we will include all the data from the  $i$ th to the 6th treatments. Repeated measures ANOVA will be performed on the included data, in which the treatment number ( $i$  to 6) is a within-subject variable and sex is an independent variable. If no significant main effect of treatment number ( $p < 0.05$ , effect size  $> 0.8$ ) is found at the  $i$ th iteration in either the prefrontal hemodynamic activations or the memory task scores, it means the  $i$ th TILS treatment is sufficient to stabilize the veterans' prefrontal activity and the rest treatments are not necessary. Thus, the  $i$ th TILS treatment will be determined as the optimal dosage for treating the veterans with PTSD.

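### The Aim 1 CCO model has no period or order term; the test stays valid on average, but a visit difference in CCO response would cost power and could move the realised TILS-sham estimate

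*SAP*

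**What the plan says.** The Protocol's account of the first two treatment visits states: "we will administer a sham treatment and a TILS treatment in a randomized sequence during the first two weeks (visits 3 and 4". The wider schedule is "once weekly TILS treatment at the same light power for seven weeks (visits 3 – 9", so the two periods are one week apart. One of the effects to be compared with sham is "the prefrontal metabolic/CCO changes measured by bbNIRS during the treatment".

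The SAP's first paragraph gives the model: "The mean CCO changes during the treatment period will be analyzed with repeated measures ANOVA", with "treatment type (TILS, sham) as a within-subject variable and sex (male, female) as an independent variable". CCO is expressed as a change from an initial baseline. No visit, period or order factor is named for this analysis. The available text does not say whether order is balanced or stratified by sex, or how the treatment effect is weighted over the two sexes.

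**The concern.** Two treatments in random order over two visits make an AB/BA crossover, and the usual model for that design includes period. Without it, any change in CCO response between visit 3 and visit 4 goes to one of two places. If the orders are balanced it goes into the within-person error, which makes the test less sensitive. If they are not, part of it also goes into the TILS-sham difference.

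Visits 3 and 4 are the only sham-controlled part of the trial described, and the SAP makes oxidised CCO its focus. This test therefore carries the controlled evidence, and there is no second comparison to fall back on if it is blunted.

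**Working it through.** The plan gives no power or effect figure for Aim 1, so there is nothing of its own to reproduce. The check is an illustration under stated assumptions.

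**Model.** With two within-person levels, the repeated measures ANOVA reduces to a linear model on D = TILS minus sham:

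D = τ + s·p + e, with SD(e) = 1

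Here s = +1 if TILS is at visit 4 and −1 if it is at visit 3. p is the visit 4 minus visit 3 shift in CCO response, in SDs of the within-person TILS-sham difference.

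- SAP model: D on sex, N − 2 error df.
- With period: D on sex and s, N − 3 error df.

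**Assumed, not in the documents.** N = 20; 16 men and 4 women; two-sided 5% test; treatment effect weighted equally over the sexes (Type III). The true effect is 2.8 standard errors: SE = ½√(1/16 + 1/4) = 0.280, so τ = 0.783.

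**1. Loss of power, orders balanced within sex (men 8:8, women 2:2).** The estimate does not move. The expected residual mean square of the SAP model rises from 1 to 1 + p²·N/(N − 2). At p = 0.5 that is 1 + 0.25 × 20/18 = 1.28; at p = 0.8 it is 1 + 0.64 × 20/18 = 1.71. Simulation (at least 60,000 trials per row) gives:

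| p | Power, SAP model | Power, with period | Type I error, SAP model |
|---|---|---|---|
| 0 | 75% | 75% | 4.8% |
| 0.2 | 74% | 75% | 4.6% |
| 0.3 | 72% | 75% | 4.2% |
| 0.5 | 66% | 75% | 2.8% |
| 0.8 | 53% | 75% | 1.2% |

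The SAP test becomes conservative, not liberal. Other assumed sizes at p = 0.5 give 61% vs 70% (8 men, 4 women), 67% vs 75% (10 and 10) and 70% vs 78% (32 and 8).

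**2. Simple randomisation of order (16 men, 4 women).** Power without vs with the term is 75% vs 73% at p = 0, 72% vs 72% at 0.3 and 66% vs 73% at 0.5. Break-even is near p = 0.25. Type I error of the SAP model, averaged over orders, stays at about 5%.

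**3. Movement of the realised estimate.** Let b be the share of veterans with TILS second minus the share with TILS first, within a sex. The equally weighted estimate moves by p·(b_men + b_women)/2. An estimate weighted by numbers moves by p times the overall b.

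- 10 men and 10 women, 7 of 10 TILS-second in each sex: b = 0.4 in both. At p = 0.5 the estimate moves by +0.20, and the type I error for that realised split is 9.5% (5.0% with the term).
- 10 and 10, with 7 of 10 TILS-second in men and 3 of 10 in women: (0.4 − 0.4)/2 = 0. The main effect does not move.
- 16 and 4, TILS second:first 9:7 in men and 1:3 in women (10:10 overall): (2/16 − 2/4)/2 = −0.1875. At p = 0.5 the estimate is 0.783 − 0.094 = 0.69, or 0.88 with the orders mirrored. A number-weighted test does not move here.

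**4. Cost of the term when p = 0 (noncentral t).** The added variance of the treatment estimate is b̄²/S, where b̄ is the averaged imbalance above and S = N − n_men·b_men² − n_women·b_women². Power without the term is 75.4%; with it:

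| Split | Power with period | Cost (points) |
|---|---|---|
| men 8:8, women 2:2 | 75.1% | 0.3 |
| men 9:7, women 1:3 | 74.2% | 1.2 |
| men 9:7, women 3:1 | 72.4% | 3 |
| men 11:5, women 3:1 | 69.3% | 6 |
| 10 and 10, 12:8 overall | 73.4% | 2 |
| 10 and 10, 14:6 overall | 67.7% | 8 |

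With a sex-by-order interaction as well, power at men 9:7, women 1:3 drops to 64.6%, a cost of 11 points.

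**The case against.** The case for leaving the model alone has four parts.

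- **Randomised order already deals with visit effects.** This stands as to validity. A reader might infer that omitting period biases the test or inflates its false-positive rate. Averaged over the randomisation it does neither: type I error is about 5% under simple randomisation and lower under balanced orders. The 9.5% above holds only given one particular uneven split.
- **The endpoint is a change from baseline.** If that baseline is the session's own, which is the likelier reading, a shift in level between visits cancels. Only a visit difference in the response itself matters, and the documents neither show nor exclude one.
- **The gain needs a sizeable shift.** A shift of 0.5 is 64% of the assumed effect (0.5/0.783). If errors are independent across visits, it is about 0.7 of the per-visit within-person SD (0.5 × √2). Under simple randomisation with little or no shift, adding the term loses 2 to 3 points.
- **Imbalance within sex matters less than it first seems.** A reader might infer that uneven orders within either sex always distort the treatment effect. They do not. At overall balance, the main effect moves only if the sex groups are unequal in size, the test weights the sexes equally, and the two imbalances do not cancel. The 9:7 and 1:3 example depends on an assumed 16/4 mix.

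All four limit the size and priority of the point. None gives a reason to leave the randomised order out of the model.

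**Conclusion.** The point holds as a cheap improvement of low to moderate priority, not as an error in the plan. The model omits period although order was randomised over two visits. If CCO response differs between those visits, the test loses sensitivity, and with uneven orders the single reported difference contains part of the visit effect.

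Under the assumed N = 20 (16 men, 4 women), with orders balanced within sex, the loss is about 3 points at a shift of 0.3, 9 at 0.5 and 22 at 0.8 SD of the within-person difference. It becomes material only from about 0.5. These figures show direction and range. They should not be read as this trial's actual loss, because N, sex mix, SD, effect, allocation scheme and shift are all assumed. Part of the SAP is not in the available text, so the absence of those details is not held against the plan.

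**What to change.** Add period (visit 3 or 4) to the Aim 1 CCO model. Within the existing repeated measures ANOVA, the equivalent is to add order (sham first or TILS first) as a between-subject factor, whose interaction with treatment carries the period effect. A mixed model is not needed. Leave out a sex-by-order interaction: small cells make it expensive, and the equally weighted treatment effect cannot be estimated if all veterans of one sex have the same order. State whether the treatment test is weighted or unweighted over sex, and report the number of veterans in each order by sex. Where the fNIRS and memory-score increments are compared with sham, use the same adjustment.

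The cost is a sentence or two in the SAP, no new data and one error degree of freedom (18 to 17 at N = 20). If there is no shift, power falls by about 0 to 3 points with balanced or mildly uneven orders, and by 6 to 8 when they are markedly uneven. The period term does nothing about carryover from the first visit to the second, which is a separate question.

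### Aim 2 judges stable up-regulation only from within-visit changes, so with a roughly constant gain per session it cannot tell an effect lost within a week from one still accumulating

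*SAP*

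**What the plan says.** The last paragraph of the Protocol sets the Aim 2 question: to "determine the least number of TILS sessions that can stably up-regulate prefrontal activity, which will be considered as an optimal TILS dosage". Sessions are weekly and "each veteran will receive a total of six TILS treatments". Table 1 gives the same sequence for each Aim 2 visit (5 to 9): "Pre-treatment fNIRS scan TILS; bbNIRS measurement Post-treatment fNIRS scan". Visits 3 and 4 have the same pair of scans around one sham and one TILS session, in random order.

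The SAP (Statistical Analysis Plan, second paragraph) judges the ith treatment "by interrogating the veterans' incremental changes (post-treatment minus pre-treatment) in the prefrontal activations and behavioral scores in the three memory tasks". The Protocol uses the same term for visits 3 and 4 and spells it out as "post-treatment measures minus pre-treatment measures". For treatments i to 6, "Repeated measures ANOVA will be performed on the included data", with session number varying within veterans and sex between them. The decision step begins "If no significant main effect of treatment number ( $p < 0.05$ , effect size $> 0.8$ ) is found", and the ith treatment is then held to be "sufficient to stabilize the veterans' prefrontal activity and the rest treatments are not necessary".

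No step in the supplied text compares pre-treatment scans across weeks or with the level before the first treatment. The initial baseline mentioned in the SAP's first paragraph belongs to the HbO2, Hb and CCO concentrations, not to the Aim 2 activations and memory scores.

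**The concern.** The question is about a state that repeated weekly sessions produce. The outcome is the response within one visit. A gain carried over from earlier sessions raises that visit's pre-treatment scan and is then subtracted, so the increment does not show whether anything lasted. Pre-treatment scans taken a week or more after a TILS session are the measurements that carry this information, yet the rule uses them only as the quantity subtracted.

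This is a separate matter from whether increments are tested against zero or sham. Even if every increment were shown to be positive, they would not show whether the effect persists or builds. What is at stake is Aim 2's main product, the chosen number of sessions, together with the claim that further sessions add nothing.

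**Working it through.** The supplied text gives no sample size, SD or expected gain for Aim 2, so there is no planned figure to reproduce.

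**Inputs from the documents.** Six weekly TILS sessions; pre- and post-treatment scans at each visit; outcome post minus pre; repeated measures ANOVA over sessions i to 6 with sex between veterans; criterion p < 0.05 with effect size > 0.8, metric not named.

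**Algebra.** Let a share r of the level carry over to the next session, and let each session add d. Then pre_k = r × post_(k−1) and post_k = pre_k + d, so post_k − pre_k = d for every r from 0 to 1. The expected increment does not depend on r, and a larger sample cannot change that.

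**Numbers.** Assume d = 0.8 in units of the SD of the change score.

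| Carry-over r | Increment, sessions 1 to 6 | Pre-treatment level at session 6 | Post-treatment level at session 6 |
|---|---|---|---|
| 0 | 0.8 each | 0 | 0.8 |
| 0.5 | 0.8 each | 0.78 | 1.58 |
| 1 | 0.8 each | 4.0 | 4.8 |

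With r = 1, stopping after session 1 leaves the level at 0.8 of 4.8, which is one-sixth of the six-session gain.

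**What the rule selects.** It was simulated with assumed N = 10, 20, 30 and 40, 2,000 runs per cell, stopping at the first i where no outcome shows a main effect.

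- One outcome, p < 0.05 alone: session 1 in about 95% of runs at each r (theory 1 − 0.05 = 0.95).
- Two independent outcomes, p < 0.05 alone: 0.90–0.91 (r = 0), 0.90–0.91 (r = 0.5) and 0.89–0.91 (r = 1). Theory is 0.95² = 0.9025.
- Two outcomes with effect size > 0.8 also required, read as Cohen's f or partial eta-squared: 0.998–1.00 at each r.

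Whatever the metric, a second condition for significance can only make session 1 more likely. The SAP does not say how the three tasks are combined. With k independent tests the p-only figure is 0.95^k, but it is the same at every r.

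**Boundary check: full retention, shrinking gains.** With increments 0.8, 0.4, 0.2, 0.1, 0.05, 0.03 and two outcomes, p < 0.05 alone gives session 1 in 0.50, 0.19, 0.04 and 0.01 of runs (N = 10, 20, 30, 40). With a slower decline (0.8, 0.64, 0.51, 0.41, 0.33, 0.26) it is 0.73, 0.51, 0.33 and 0.19. With the effect-size condition (f or partial eta-squared) it is 0.95–1.00 in both. The p-only rule therefore does respond to session number when gains are not constant.

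**Does the retained level separate the cases?** The same simulation tested one pre-treatment outcome across the six sessions at p < 0.05. A session effect was found in about 5% of runs with no retention; in 0.55, 0.90, 0.99 and 1.00 with half retained (N = 10, 20, 30, 40); and in 1.00 with full retention at every N. This run did not model the sham/TILS sequence, practice or drift.

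**The case against.** **Stability may mean that the response has stopped changing.** Neither document calls the effect lasting or cumulative, and flat increments might be meant as a plateau. That reading works only if increments are flat near zero while the pre-treatment level is raised, and the rule requires neither. Declaring later sessions unnecessary is also a claim about what has been kept.

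**Gains may not be constant.** This stands and limits the point. A reader might infer that the rule gives the reverse of the right answer, because a durable effect that closes the deficit makes increments shrink and so counts as not yet stable. The documents do not support that. If each session closes half the remaining deficit, session 1 leaves half of it open, so moving on is reasonable. In the faster shrinking case on p alone, the rule chose session 2 or 3 in 69%, 81% and 82% of runs at N = 20, 30 and 40 (1,381, 1,625 and 1,642 of 2,000). By then 1.2/1.6 = 75% or 1.4/1.6 = 87.5% of the deficit is closed. With the effect-size condition read as f or partial eta-squared, the rule mostly picks session 1 there too, so that argument would also hang on an undefined metric.

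**Levels between visits are noisier and confounded.** This stands. Memory tasks are repeated throughout and there is no sham after visit 4, so practice or time alone can raise pre-treatment levels. A same-visit change removes drift between visits. Hence the retained level should be added to the increment and should not replace it.

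**Not every later pre-treatment scan shows TILS retention.** A reader might assume that all scans from visit 4 do. For sham-first veterans the visit 4 pre-treatment scan follows sham only.

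**Part of the SAP was not available.** An analysis of levels elsewhere in it cannot be excluded. The decision rule itself is complete as written and uses increments alone.

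**Conclusion.** The concern holds for a roughly constant gain per session. The Aim 2 rule then receives the same expected data whether nothing or everything is retained, and it favours session 1 equally in both cases. That result is algebra and needs no assumed sample size. The selection frequencies do rest on assumed N, SD and gain, on independence of the two outcomes, and on how the effect size is read. The one-sixth figure applies to full retention with equal gains; the documents do not predict that pattern. It does not follow that the rule fails under every pattern of response, or that the within-visit change is a wrong outcome for the acute effect. The point should be settled before analysis, because as written Aim 2 cannot support a conclusion about stable up-regulation.

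**What to change.** Keep the within-visit increment as the acute-response outcome. Add to the Aim 2 rule an analysis of the retained level, specified as follows:

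- Outcome: pre-treatment activation and memory score, as change from the visit 3 pre-treatment scan. The visit 2 scan should not be the reference, because veterans are selected on it.
- Index: number of TILS treatments already received, with the sham/TILS sequence in the model. The visit 4 pre-treatment scan reflects TILS only in TILS-first veterans, and their visit 5 pre-treatment scan comes about two weeks after their only TILS session. From visit 5 to visit 9 both sequences have received one to five treatments.
- Conclusion: call a session number enough for stable up-regulation only if the retained level has risen and then stopped rising.
- Limits to state: retention after the sixth treatment is not observed, since the supplied text schedules no scan after visit 9. Rises in level, especially in memory scores, cannot be separated from practice or time trends.

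The cost is SAP wording and one more model on scans already scheduled, with no new visits. The downsides are noisier between-visit levels and a retained level that can be assessed only after treatments 1 to 5.

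### The session-number rule includes i = 6, where the ANOVA has one level and no test exists, and it has no outcome for stability not being reached within six treatments

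*SAP*

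**What the plan says.** The goal, in the last paragraph of the Protocol, is to find "the least number of TILS sessions that can stably up-regulate prefrontal activity". The Protocol also says that "each veteran will receive a total of six TILS treatments", so there is no seventh session to compare with the sixth.

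The second paragraph of the Statistical Analysis Plan gives the rule:

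- The question at each step is whether the i-th "treatment ( $i \leq 6$ ) is sufficient to stably up-regulate" prefrontal activation and functioning. The value i = 6 is therefore inside the range.
- The data at step i are those from treatment i "to the 6th treatments. Repeated measures ANOVA will be performed on the included data, in which the treatment number" is the within-subject factor, with sex as the between-subject factor.
- The trigger is a null result: "If no significant main effect of treatment number ( $p < 0.05$ , effect size" above 0.8). If no such effect is found, treatment i is declared sufficient and becomes the optimal dosage.

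The effect-size metric is not named. Neither document treats i = 6 separately, and neither gives an outcome for failure to stabilise within six treatments.

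**The concern.** The rule compares treatment i with the treatments after it. At i = 6 there are none, so nothing can be compared, yet the SAP lists i = 6 among the values that can be declared sufficient.

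The order of the steps makes this more than a technicality. Because the aim is the least number, the rule moves forward and stops at the first i without a significant effect. It gets to i = 6 only if iteration 5, which compares treatment 5 with treatment 6, met the plan's criterion for change. The last usable evidence then says that the response was still moving, and the literal rule answers that six treatments are enough to stabilise it.

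At stake is the session-number conclusion of Aim 2. As written, the analysis cannot report that stability was not shown.

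**Working it through.** **Inputs from the documents.** Six TILS treatments (one in visits 3–4 plus five in visits 5–9: 1 + 5 = 6); i up to and including 6; data from treatment i to treatment 6; two sex groups; criterion p < 0.05 with effect size > 0.8. The available text gives no sample size, power or SD, so there is no stated figure to reproduce.

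**Step 1: degrees of freedom.** Levels at iteration i = 6 − i + 1 = 7 − i. Numerator df = 6 − i. Error df = (N − 2)(6 − i).

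| i | 1 | 2 | 3 | 4 | 5 | 6 |
|---|---|---|---|---|---|---|
| Levels | 6 | 5 | 4 | 3 | 2 | 1 |
| Numerator df | 5 | 4 | 3 | 2 | 1 | 0 |

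At i = 6 the error df is (N − 2) × 0 = 0 for any N. Fitting a repeated measures ANOVA to one-level data returns an undefined F and an undefined p on 0 and 0 df. This step needs no assumption.

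**Step 2: how often i = 6 is reached.** Every input here is assumed: one outcome, compound symmetry, within-subject SD of 1, N = 12 to 40, and a mean increment that rises by a constant amount at every session, so that no plateau exists. The forward rule was simulated. The table gives the share of trials that pass iterations 1 to 5 and so return i = 6 on the literal reading. The first figure is for N = 12 and the second for N = 40.

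| Rise per session (within-subject SD) | p < 0.05 alone | with 0.8 as Cohen's f | with 0.8 as partial eta-squared |
|---|---|---|---|
| 0.5 | 18% to 59% | 5% to 0.1% | almost never |
| 0.7 | 32% to 86% | 17% to 5% | almost never |
| 1.0 | 61% to 99% | 42% to 32% | almost never |
| 1.4 | 88% to 100% | 79% to 87% | almost never |

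Taking sex out of the error term moves the Cohen's f figures by several points at N = 12 and leaves the pattern unchanged.

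**Step 3: why the metric matters so much.** At iteration 5 there are two levels that differ by δ. The effect sum of squares is about N × 2 × (δ/2)² = Nδ²/2, and the error sum of squares is about N. So f ≈ √(δ²/2) = δ/√2, and partial eta-squared = f²/(1 + f²).

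| δ | f ≈ δ/√2 | partial eta-squared |
|---|---|---|
| 0.5 | 0.35 | 0.125/1.125 = 0.11 |
| 0.7 | 0.49 | 0.245/1.245 = 0.20 |
| 1.0 | 0.71 | 0.5/1.5 = 0.33 |
| 1.4 | 0.99 | 0.98/1.98 = 0.49 |

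For the first three slopes f lies below 0.8, so a larger N makes passing iteration 5 rarer. For the fourth it lies above 0.8, so a larger N makes it more common. Partial eta-squared is below 0.8 throughout. This matches the direction of each row in Step 2.

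**Step 4: the other no-plateau trials.** At 0.5 SD per session, 100 − 18 = 82% (N = 12) to 100 − 59 = 41% (N = 40) stop at i ≤ 5 on p alone. With Cohen's f, 100 − 5 = 95% to 100 − 0.1 = 99.9% do. They stop because non-significance, or an effect below the threshold, is read as stability.

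**The case against.** Four points can be made for the plan.

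1. **An ANOVA that cannot be run finds nothing, so i = 6 may return no result.** The SAP can fairly be read as requiring a test that was actually performed. A reader might infer that the rule always ends in a number declared sufficient; that holds only on the literal reading. On the other reading the rule has no defined result at i = 6. The gap remains, but it is then an undefined endpoint and not a guaranteed wrong answer.

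2. **The p-only frequencies do not describe the SAP's rule.** This stands. The criterion also has the 0.8 condition. A reader might infer that up to 59% or 86% of no-plateau trials would default to six at the moderate slopes (0.5 and 0.7 SD). The documents do not support this: at those slopes the Cohen's f reading cuts the figures to 5% or less and 17% or less, and partial eta-squared nearly removes them.

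3. **Most wrong declarations come from elsewhere.** This also stands at moderate slopes. Even on the literal reading, the lack of any negative result should not be put down mainly to i = 6, because many no-plateau trials stop earlier by accepting a null result.

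4. **One outcome was simulated, whereas the SAP looks at activation and at memory scores.** If a null result in either outcome is enough to stop, i = 6 is reached less often than shown; if both must be null, more often. The wording permits both. At i = 6 it makes no difference, because neither outcome can be tested.

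It might also be said that six is simply the most that was given. But the SAP labels the selected number as sufficient and optimal, and reaching the last session does not show stability.

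**Conclusion.** The point holds as a defect in the decision rule. At i = 6 there is one level, 0 numerator df and no test; this follows from the SAP's own definitions for any N, SD or effect-size metric. Read literally, treatment 6 is declared sufficient just after treatments 5 and 6 met the criterion for change. Read otherwise, the rule gives no answer. On both readings the outcome of no stable number within six treatments is missing.

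The frequency cannot be fixed from the documents. Across the assumed settings it runs from almost never to nearly always, depending on N, slope and the unnamed metric, so no single percentage should be quoted as the size of the problem. Reading non-significance as stability at i ≤ 5 is a separate weakness.

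**What to change.** In the iterative paragraph of the SAP, restrict the tested range to i = 1 to 5. Add that if iteration 5 (treatment 5 versus treatment 6) still meets the criterion for change, the conclusion is that no stable session number was identified within six treatments, and that i = 6 is not selected by default.

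This costs one or two sentences and needs no extra data, visits or participants. The only downside is that a negative conclusion becomes possible. The change does not cure early stopping on a non-significant result, which needs its own remedy.

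### The session-by-session repeated measures ANOVA has no stated missing-session rule or sphericity correction; a mixed model on all available sessions would be a cheap improvement, test by test

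*SAP*

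**What the plan says.** The second paragraph of the SAP's section Statistical Analysis Plan sets out an iterative procedure over the six TILS treatments. At iteration i, "we will include all the data from the" ith treatment through the last, and "Repeated measures ANOVA will be performed on the included data", with treatment number within veterans and sex between them. The outcomes are post-minus-pre changes in prefrontal activation and in scores on three memory tasks. The decision rule opens "If no significant main effect of treatment number". An effect counts if p < 0.05 and the effect size exceeds 0.8, and the metric of that effect size is not named. If no such effect is found, session i is taken as enough. The protocol gives the purpose: to "determine the least number of TILS sessions that can stably up-regulate prefrontal activity".

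Under the protocol, veterans are instructed to "receive once weekly TILS treatment at the same light power for seven weeks". The investigators will "administer a sham treatment and a TILS treatment in a randomized sequence during the first two weeks", so TILS treatments 1 and 2 are one or two weeks apart depending on the order drawn. Activation is an outcome "which will be measured by fNIRS before and after the treatment", and the later visits run "with fNIRS and bbNIRS measurements taken in each visit".

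The supplied text has no rule for a missed visit or an unusable recording and does not say whether a missed visit is made up. It names no sphericity correction or covariance structure. It gives no sample size, loss rate or within-veteran correlation.

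**The concern.** Two separate weaknesses meet at the first test, which decides whether session 1 is returned as sufficient.

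**Missing sessions.** In its usual form, repeated measures ANOVA needs a full row of data from each veteran. For activation at i = 1 that is 6 sessions × 2 scans = 12 usable scans; memory scores can survive an unusable scan. A veteran short of one session is dropped and the observed sessions go unused. At i = 5 only two sessions are needed, so under intermittent loss the first test loses most. Since failing to reject is the positive finding here, lost precision pushes the p-value towards a declaration of sufficiency.

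**Sphericity.** With up to six weekly measurements, neighbouring sessions may well correlate more than distant ones. The uncorrected F test then rejects too often. That pushes the other way, and it cannot arise at i = 5, where there are only two levels.

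**Working it through.** The plan gives no sample size, power or loss figure, so there is nothing of its own to reproduce.

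**Inputs from the documents:** six TILS sessions; tests at i = 1 to 5 (at i = 6 one session is left and nothing can be compared); alpha 0.05; effect size above 0.8; a one- or two-week gap between TILS 1 and 2.

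**Assumed:** intermittent loss m = 5–10% per session, or dropout d = 5–10% per interval; serial correlation 0.5–0.9; N as stated at each step.

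**1. Complete veterans, intermittent loss.** Share = (1 − m)^(7 − i).
- i = 1: 0.95^6 = 0.735; 0.90^6 = 0.531.
- i = 5: 0.95^2 = 0.902; 0.90^2 = 0.810.

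**2. Standard error of a session difference, complete cases.** Inflation = 1/√share, which does not depend on N or on the effect.
- i = 1: 1/√0.735 = 1.166; 1/√0.531 = 1.372.
- i = 5: 1.053; 1.111.
- Collected sessions discarded at i = 1: 1 − (1 − m)^5 = 22.6%; 41.0%.

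**3. The same standard error with all available sessions.** Expected information was computed over all 15 session pairs, for compound symmetry 0–0.9, serial correlation 0.5–0.9, and serial correlation 0.5 plus a veteran effect.
- Average inflation: 1.018–1.031 at 5% loss; 1.039–1.066 at 10%.
- Worst pair: 1.039 and 1.082.
- Hand check with uncorrelated sessions: 1/√0.95 = 1.026; 1/√0.90 = 1.054.

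**4. Pure dropout instead.** Every iteration needs session 6, so all keep the same completers: (1 − d)^5 = 0.774 or 0.590 at every i, with standard error up 14% or 30%. With all sessions the average rise is 7–8% or 15–18%. The gain is then in early-session comparisons, and the excess loss at i = 1 relative to i = 5 disappears.

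**5. False positives at i = 1, p-value alone.** Null simulation with N = 20, ten of each sex, half the veterans with the two-week gap, and 3,000 trials per cell (Monte Carlo error about 0.4 points). Each cell shows no loss / 10% loss, in %.

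| Serial correlation | Uncorrected ANOVA | Greenhouse-Geisser | Mixed model, Kenward-Roger |
|---|---|---|---|
| 0.5 | 6.2 / 6.6 | 3.4 / 3.2 | 5.6 / 5.3 |
| 0.7 | 7.9 / 6.9 | 4.6 / 3.4 | 4.8 / 5.7 |
| 0.9 | 8.3 / 8.6 | 4.0 / 4.1 | 4.6 / 5.4 |

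The mixed model here had sex and sequence as fixed effects but no sex-by-treatment-number term. A separate complete-data simulation (N = 20, 6,000 runs) gave 6.6, 7.2 and 8.8% for the uncorrected ANOVA.

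Two tempting shortcuts fail:
- A compound-symmetry mixed model under the same three correlations, without loss, gives 6.3, 8.3 and 8.3% at i = 1 and 1.7, 0.6 and 0.5% at i = 5.
- A Wald chi-square test from a serial-correlation model at 10% loss rejects 6.5–7.9% at n = 12 and 5.5–6.9% at n = 20.

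**6. Adding the effect-size condition.** If 0.8 is Cohen's f (assumed), partial eta-squared must exceed 0.64/1.64 = 0.390. The joint false-positive rate at six sessions is then at most 0.3%, corrected or not (n = 12 to 40).

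**7. Effect on the decision, p-value alone.** Assumed: mean rising 0.3 SD per session to session 3, then flat; serial correlation 0.6; 10% loss; 600 runs (error up to 2 points). Session 1 wrongly declared sufficient at n = 12 / 20 / 40:
- complete-case uncorrected ANOVA: 81 / 68 / 40%
- complete-case Greenhouse-Geisser: 92 / 80 / 54%
- mixed model with serial correlation, F test on within-subject degrees of freedom: 76 / 58 / 24%

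**The case against.** **Complete-case deletion is not in the plan.** True. It is inferred from the named method, and the phrase about including all data could be read the other way. Every loss rate is assumed. Silence can be claimed only for the supplied text, from which part of the SAP is absent. If missed visits are made up, gaps would come mainly from unusable recordings. What remains is that the text names a method which usually needs full rows and gives no rule for incomplete ones.

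**The 6–9% ignores the effect-size condition.** This stands. Under Cohen's f the sphericity inflation is largely immaterial. The missing-session gap remains on any reading.

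**A reader might infer that missing sessions must drive the plan to stop at session 1.** The documents do not support that. Loss makes non-significance on the p-value easier, but the full rule also has the 0.8 condition. Read as Cohen's f, loss can act the other way, because sample f grows as n shrinks: with a real change and n = 20, rejection rose from 0.4% without loss to 4.8% at 10% loss. The net direction is open until the metric is defined.

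**A reader might infer that adding Greenhouse-Geisser is an equally good repair.** It is not. It controls false positives, but under a rule that rewards non-significance it raises wrong declarations at session 1 (68% to 80% at n = 20 above).

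**This is secondary to reading non-significance as sufficiency.** Largely fair. The mixed model reduces the wrong-decision rate in that scenario but leaves it at 24–76%.

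**Conclusion.** The point holds as a cheap improvement. The supplied text leaves missed sessions and sphericity unaddressed in a procedure of up to six repeated measurements. At an assumed 5–10% intermittent loss, and if incomplete veterans are dropped, the first test would run on 74–53% of veterans with standard errors up 17–37%. A model using every observed session would average about 2–7%. The sphericity effect (about 6–9% against 5%) concerns the p-value alone, rests on N = 20 and serial correlation 0.5–0.9, and may not matter once the effect-size condition is defined.

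A reader might infer that the mixed model secures the trial's error rate. It does not. The evidence is per test, at small assumed N, with a small-sample degrees-of-freedom method, and multiplicity over iterations and outcomes is untouched. Nor does the model cure the non-significance rule or the unequal power across iterations. With complete data, N = 30, a drift of 0.1 SD per session and correlation 0.5 (all assumed), power falls from 0.68 at i = 1 to 0.08 at i = 5.

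**What to change.** Replace the iterative ANOVA with one REML linear mixed model per outcome on all available sessions 1 to 6, and state in the SAP:

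- **Fixed effects:** categorical treatment number, sex, sex by treatment number, and sham/TILS sequence. The interaction keeps the hypothesis aligned with the planned ANOVA when the sexes are unequal in number.
- **Covariance:** a veteran random effect plus serial correlation indexed by visit week (for example spatial power), because the TILS 1 to 2 gap varies with the sequence. Compound symmetry alone would keep the sphericity assumption.
- **Inference:** Kenward-Roger degrees of freedom. For i = 1 to 5, test the joint contrast, averaged over sex, that the means of sessions i to 6 are equal.
- **Effect size:** define the 0.8 metric on the model scale.
- **Missing sessions:** say how a missed visit is numbered in the analysis, and report veterans and usable sessions at each iteration.
- **Fallback if the model fails:** drop the random effect first. If Greenhouse-Geisser ANOVA is kept as a last resort, state that it makes wrong declarations of sufficiency at session 1 more likely under this rule.

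The cost is SAP wording and standard software, with no new data. The downside is that the covariance and its fallback must be chosen in advance, and sessions are assumed missing at random given what was observed. The exact model with the interaction term should be simulated at the trial's actual N before it is fixed. The non-significance rule, unequal power and multiplicity need separate changes.
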